## I. Purpose, Background and Rationale

### A. Aim and Hypotheses

1. **Brief Introduction:** Despite widespread awareness of significant negative health consequences, cigarette smoking remains the leading cause of preventable morbidity and mortality in the US (Creamer et al., 2019; Jamal, 2018). Moreover, the highest rate of smoking and heaviest burden of smoking-related illness occurs among low-socioeconomic status (SES) individuals relative to higher SES groups (Businelle et al., 2010; Clegg et al., 2009). Low SES individuals are also 40% less likely to succeed in quitting smoking when they attempt to do so (National Center for Chronic Disease Prevention and Health Promotion (US) Office on Smoking and Health, 2014). One potential explanation for the disparity in rate of smoking and successful quit attempts may be differences in individual rates of delay discounting (DD), i.e., the degree to which rewards loses their value as the delays to their receipt increase (Odum, 2011). A proposed way to reduce steep DD and, potentially, substance use has been computer training for working memory, which has shown favorable results in a sample of individuals with stimulant dependence (Bickel et al., 2011) and substance use broadly (Felton et al., 2019), with the latter even showing decreases in cigarette smoking in a subset of the sample.
2. **Aims:** The current study will assess delay discounting (DD), working memory (WM) training, and cigarette smoking cessation outcomes. The aims of the project are the following:
  - Assess efficacy of WM training
    - Assess efficacy of WM training on cigarette smoking
    - Assess efficacy of WM training on DD

## B. Background and Significance

1. Study Significance: The development of effective, theoretically coherent interventions addressing cigarette smoking is imperative, particularly interventions that would be feasible, efficacious, and acceptable in low-SES individuals. The proposed research is an innovative approach that capitalizes on previous findings showing reductions in delay discounting and even cigarette smoking. If working memory training is found to improve smoking cessation outcomes as a function of reductions in delay discounting, the project results could be helpful in future development of low-cost interventions for cigarette smoking.
2. The highest rate of smoking and heaviest burden of smoking-related illness occurs among low-SES individuals (Businelle et al., 2010; Clegg et al., 2009). One explanation for this disparity may be differences in individual rates of DD, which have been shown to be reduced with working memory training. (Bickel et al., 2011; Felton et al., 2019). Given the low cost of administering working memory training, such an intervention may be favorable for low-SES populations to improve smoking cessation outcomes.
3. Literature Review: DD has significant associations with:
  - **Cigarette smoking** (smokers tend to have higher rates of DD compared to non-smokers; Bickel et al., 1999);
  - **Smoking treatment outcome** (individuals who remained smoke free after a smoking cessation intervention had lower DD compared to those who didn't; González-Roz et al., 2019; Krishnan-Sarin et al., 2007; MacKillop & Kahler, 2009; Yoon et al., 2007);
  - **SES** (individuals with lower education and income have higher DD rates compared to those who are more educated and affluent; de Wit et al., 2007; Reimers et al., 2009).

An innovative way to reduce DD that has been proposed is via working memory (WM) training. WM refers to one's capacity to hold information while engaging in complex mental tasks, including reasoning, comprehension, and learning (Baddeley, 2010). Previous research has shown that DD and WM correlate negatively (Shamosh et al., 2008), that individuals with higher DD rates show neural deficits in WM (Herting et al., 2010), and that acute nicotine abstinence is associated with WM deficits (Mendrek et al., 2006; Patterson et al., 2010). Furthermore, previous studies targeting WM to reduce DD have shown favorable results in a sample of individuals with stimulant dependence (Bickel et al., 2011) and substance use broadly (Felton et al., 2019), with the latter even showing decreases in cigarette smoking in a subset of the sample.

## C. Rationale

1. Although previous research has shown WM training to reduce DD, and cigarette use in a small subsample, the hypotheses of this study are largely exploratory. However, given the theoretical connections between DD, SES, and WM, it is expected that the hypotheses of this project will be supported.

2. The performance of this project may advance our knowledge of the relevant clinical targets for smoking cessation in low-SES individuals. In particular, this project is expected to shed light on DD as the putative mechanism in smoking for low-SES individuals and the durability of reductions in smoking as a result of reductions in DD through WM training.
3. Despite the evidence for some successful techniques for reducing DD, little of this work has been translated into intervention approaches to target clinical outcomes. This application seeks to capitalize on the emerging literatures indicating (1) WM training may be an effective and efficient way to reduce DD, and (2) DD is associated with SES, cigarette smoking, and treatment outcomes. Though WM training has been successfully implemented in laboratory-controlled experiments to reduce DD, we are not aware of any interventions for clinical disorders that specifically seek to do so and potentially enhance treatment outcomes.

## II. Research Plan and Design

**A. Study Objectives:** The main aims of this project are to examine the observed efficacy of WM training.

**B. Study Type and Design:** This study is an open-label trial longitudinal (participants will be assessed through their 1-month quit date) trial.

**C. Sample size, statistical methods, and power calculation**

1. Consistent with Stage 1a pilot trials, the current trial included a small sample size of completers ( $N = 15$ ) to determine the initial outcomes of the WM intervention and its perceived feasibility/acceptability.
2. DD will be estimated by fitting the hyperbolic function specified in Eq. 1 to the indifference points computed during the task in order to estimate each individual's discount rate, where  $v$  represents the discounted value of an outcome,  $V$  is the undiscounted value,  $D$  is the delay and  $k$  is the discounting parameter, which specifies the degree to which the value of a given reward is discounted when it is delayed (with higher values representing greater discounting).

$$v = \frac{V}{1 + kD}$$

Eq. 1

While  $k$  distributions tend to be skewed, post-hoc natural logarithmic transformations will be performed, which have been shown to approximate normal distributions. We will calculate  $k$  values for each magnitude (\$50, \$200, \$1000). Due to varying degrees of goodness-of-fit associated with nonlinear regression functions, we will also calculate area-under-the-curve (AUC) estimates (Borges et al., 2016). Hypotheses encompassed will be tested using Hierarchical Linear Modeling (HLM; Raudenbusch & Bryk, 2002), which allows the analysis of repeated measures and has been recommended because of its ability to: 1) accommodate missing data, 2) examine individual change over time in outcomes, and 3) include the average change and the individual variation around this average change which is especially important

in a small sample (Raudenbusch & Bryk, 2002; Singer. & Willett, 2003), even in smaller samples (Collado et al., 2019). Hypotheses encompassed within Aim 1 will be tested using Hierarchical Linear Modeling (HLM; Raudenbusch & Bryk, 2002), which allows the analysis of repeated measures and has been recommended because of its ability to: 1) accommodate missing data, 2) examine individual change over time in outcomes, and 3) include the average change and the individual variation around this average change which is especially important in a small sample (Raudenbusch & Bryk, 2002; Singer. & Willett, 2003), even in smaller samples (Collado et al., 2019).

3. Individuals who smoke cigarette and who are low in SES and receptive to a future quit attempt will be recruited for this study. Participants will be recruited from the greater Kansas City area.

**D. Subject Criteria (See Vulnerable Populations appendix, if applicable):** The subject age range will be over 18 years old. Participants will be able to participate in the study regardless of gender and race. Special populations, such as minors and pregnant women, will not be targeted for inclusion.

1. **Inclusion criteria:** To be included in this study, a participant must be 18 years of age or older, who have smoked at least four cigarettes per day for at least 6 months, are interested in quitting cigarette smoking, are at or below the federal poverty line based on persons in family/household and annual household income:

- 1 -- \$12,880
- 2 -- \$17,420
- 3 -- \$21,960
- 4 -- \$26,500
- 5 -- \$31,040
- 6 -- \$35,580
- 7 -- \$40,120
- 8 -- \$44,660
- $\geq 9$  – add \$4,540 for each additional person,

OR they or their child(ren) utilize a federal program for low-income individuals, and are willing to participate in a 5-week working memory training program as a pretreatment adjunct to behavioral group therapy.

2. **Exclusion criteria:** Participants must not indicate a severe substance use disorder according to the DSM-V with any substance other than tobacco or have any significant medical or psychiatric condition. Such conditions could include traumatic brain injury, dementia, significant learning disability, or psychotic symptoms. Participants must be at least at a 5th- grade reading level. In case that participants are excluded, they will be provided with

resources in the community and provided with contact information for the Kansas Tobacco Quitline.

3. **Withdrawal/Termination criteria:** Participants may withdraw from the study at any time without penalty. The researcher reserves the right to discontinue individuals who evidence inability to comply to study conditions. The researcher will also exclude participants if they seem at risk for COVID-19 infection.
4. Participants can partake in other studies while participating in this research study if it does not interfere with their method of smoking cigarettes.

#### **E. Specific methods and techniques used throughout the study:**

1. **Laboratory tests:** Participants will provide breath and saliva samples to confirm smoking abstinence. Breath samples will be collected using the coVita Micro+ basic Smokerlyzer and saliva samples will be collected using the NicConfirm mouth swab tests. Timing of the samples are described in the Study Procedures section. Amount cannot be readily estimated for either test. Saliva samples will only be labeled using participant ID #'s, and breath samples will be stored on the Smokerlyzer. Saliva samples will be photographed for study records and then discarded.

#### **Study Procedures**

**COVID-19 safety procedures:** These procedures will be followed for each in-person study session, and study staff will be trained prior to any data collection. Prior to departing, the project coordinator (PC) and/or research assistant (RA) will be screened for COVID-19 risk and will make sure all items and equipment (e.g., pens, laptop computers) are sanitized. The PC/RA will also wash and sanitize their hands as well as wear a surgical mask. The PC/RA will bring surgical masks and sanitizing wipes to the study location as well. The PC/RA will screen participants 24 hours before a session and at the study location prior to entering the building.

High-touch surfaces and chairs would have been sanitized before any individuals enter the space. Participants will have been screened according to aCOVID screening form. Social distancing (6 feet or more) will be enforced at all parts of the study session unless close contact is absolutely necessary. All individuals will wear a face mask unless participants need to provide breath/saliva samples.

**Note:** If at any point a participant displays behavior inconsistent with COVID-19 safety procedures (e.g., not wearing their mask properly for extended periods of time, not social distancing), they will be reminded of the procedures. If the person refuses to engage in COVID-19 safety procedures, their participation will be terminated for the day. Individuals whose participation is terminated for the day will be asked if they are willing to follow COVID-19 safety procedures for future appointments. If participants deny their intention to meet the safety procedures, their participation in the study will be terminated. These participants will be provided with resources in the community as well as with contact information for the Kansas/Missouri Quitline. In the event that a participant reports any COVID-like symptoms, participants will be asked to leave the study location and reach out to Swope Health Services for further guidance.

Upon session conclusion, the RA will collect the laptop computer from the participant and disinfect. All high-touch surfaces and chairs will also be sanitized.

After participants complete 5 or more of the working memory trainings, they can begin attending a weekly 60-minute group based on an evidence-based behavioral treatment manual (MacPherson et al., 2016, 2017). Group topics include identifying values and goals within a variety of life areas (including achieving a non-smoking lifestyle), structuring and scheduling activities according to these personal values, identifying high-risk situations and developing appropriate coping strategies, enlisting social support assertively, discussing the benefits of a non-smoking lifestyle, receiving social support from the group, and managing lapses in smoking. Participants can attend as many sessions as they would like and join groups on a rolling basis.

**Screener call:** Interested individuals will take part in a phone call (~10 minutes) with the project coordinator to determine their eligibility. The project coordinator will ensure that participants do not meet exclusion criteria, which include: not being a smoker who has smoked 4 cigarettes/day for at least 6 months, not being interested in quitting smoking, not qualifying as low-income, having significant medical or psychiatric conditions, having severe substance use disorder for any substance other than tobacco, or being below a 5th grade reading level (asked via a self-report of educational attainment). Participants would qualify as low-income if they are at or below the federal poverty line for their respective household size OR if they or their child utilize a federal program for low-income individuals (e.g., Supplemental Security Income, Supplemental Nutrition Assistance Program, Children's Health Insurance Program, etc.); <https://aspe.hhs.gov/topics/poverty-economic-mobility/poverty-guidelines/frequently-asked-questions-related-poverty-guidelines-poverty>. Participants will be screened on any alcohol and drug use within the past 12 months and DSM-5 SUD symptoms will be assessed for any frequent substance use (2-4 times a week or more for any non-prescribed drug, 3-5 times a week or more for alcohol) other than tobacco. Participants who do not meet eligibility requirements will be informed that they will not be able to continue with the study, but the reason for this will not be disclosed. This is to ensure that participants do not attempt to alter their responses on disqualifying criteria in order to continue with the study. Contact information, in whatever medium the participant chooses (e.g., email, phone call, SMS text), and contacting preferences (e.g., medium, time of day) will also be collected for future session scheduling purposes. All individuals will be provided with a referral document which lists medical, substance use, and case management services in the Kansas City area. Individuals will be asked if they would like to receive the document over email, sent through mail, texted via SMS, or have it read out loud to them over a phone call.

**Baseline session:** This session will take approximately 1 to 1.5 hour to complete and will include informed consent and initial assessments. Participants will complete an informed consent process, which will include time and space to read the informed consent form (ICF), followed by thorough discussion with a study staff member about the nature of the study, potential risks and benefits, and participant rights. If the individual wishes to continue following this discussion, they will digitally sign the ICF via Qualtrics. At the point at which the ICF is signed by the individual, s/he will be considered an enrolled participant. Participants will also report demographic information (age, sex, race/ethnicity, current income, employment, and education level) and report on their cigarette smoking behavior. If at any point during the study a participant reports elevated suicidality, they will be thoroughly assessed for suicidality risk by the PI, who has extensive clinical experience, and participants will be referred to immediate care (e.g., Emergency department, Kansas City crisis response) depending on level of risk. All individuals will be provided with a referral document which lists medical, substance use, and case management services in the Kansas City area. Participants will also complete a reading test (Wide Range Achievement Test-4; WRAT-4) to confirm reading level from self-reported educational attainment.

Training sessions will take approximately 30 minutes to complete, will occur 2–3 times per week, and completed in 3-5 weeks in most instances. Each participant will be assigned a unique computer login for the self-guided training sessions, and progress (attendance, performance) will be monitored.

**BA groups:** Once participants complete 50% or more of their training sessions, the project coordinator will work with participants to find a time to begin the behavioral group sessions with the PI (i.e., Clinician), who will administer the intervention, over Zoom.

1. Session 1: Clinician will let everyone introduce themselves, go over group guidelines (including confidentiality), explain program rationale (engaging in pleasurable, smoke-free activities improves chances of quitting smoking), make note of barriers and benefits to quitting smoking, provide a copy of the National Cancer Institute *Clearing the Air* pamphlet, discuss previous quit attempts with the group participants as well as the upcoming quit attempt as part of the program, and introduce the Daily Activity, Mood, and Smoking Log, which asks participants to list hour-by-hour what they did during each day, the enjoyment of activity/event, the importance of it, the number of cigarettes smoked during each activity/event, and the overall mood of the day.
2. Session 2: Clinician will go over participants' use of the Daily Activity, Mood, and Smoking log, explain Life Areas, Values, and Activities (LAVA; major life areas, such as social relationships, and activities to strengthen those areas, such as spending more time with family on weekends), and ask participants to choose 15 activities related to their life areas and rank them by difficulty to accomplish.

3. Session 3 (1 week pre-quit date): Clinician will go over participants' use of the Daily Activity, Mood, and Smoking log, review participants' LAVA inventory, explain how to plan activities and integrate them with their daily log, discuss high-risk situations for relapse and how to identify them, and scheduling the quit date (and what to do in case of a "slip," i.e., smoking after quit date).
4. Session 4 (quit week): Clinician will go over participants' use of the Daily Activity, Mood, and Smoking log, discuss quit dates and quitting experience (e.g., withdrawal and immediate plans) for each participant, discuss success in accomplishing LAVA activities, identify obstacles to abstinence, offer support, talk about maintaining a healthy lifestyle (i.e., proper diet and exercise), and highlight social support, particularly by encouraging participants to form a "Contract" with a supportive person in their life (i.e., ask someone to take part in an activity with them to help them remain abstinent, such as riding bicycles together).
5. Session 5: Clinician will go over participants' use of the Daily Activity, Mood, and Smoking log, participants' contracts, quitting experience (e.g., withdrawal symptoms), strategies to avoid smoking, perceived benefits and disadvantages to quitting smoking, and identifying high-risk situations.
6. Session 6: Clinician will go over participants' use of the Daily Activity, Mood, and Smoking log, quitting experience (e.g., withdrawal symptoms), strategies to avoid smoking, perceived benefits and disadvantages to quitting smoking, discuss time management as a tool for abstinence, help identify high-risk situations, and offer support.
7. Session 7: This session will mirror Session 6.
8. Session 8: This session will mirror Sessions 6 & 7, and will include a discussion on developing a post-program plan to maintain abstinence by engaging and monitoring activities after the BA group and dealing with negative feelings, triggers, and immediate cravings. The clinician will also review the overall program progress and remind participants about the upcoming follow-up sessions.

**Post-training session:** This session is expected to take 1 to 1.5 hours to complete. 2-3 days following their last training session, participants will complete the DD task, TLFB, TOH, HVLT-R, LNS, and provide a CO breath sample. Participants will be asked to set a quit date for their cigarette smoking at this session and will be encouraged to connect to the tobacco quitline ([name]).

**1-week post quit date session:** This session is expected to take about 30 minutes to complete. Around 7 days after their quit date, participants will complete the DD task, TLFB, and provide a CO breath sample. Participants will also provide a saliva sample to test for salivary cotinine, a metabolite of nicotine to biochemically verify smoking status/abstinence.

**1-month post quit date session:** This session is expected to take about 45 minutes to complete. Around 30 days after their quit date, participants will complete the DD task, TLFB, TOH, HVLT-R, LNS, provide a CO breath sample, and provide a saliva sample.

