### **C. Informed consent process and timing of obtaining of consent:**

1. The project coordinator ([name]) will give subjects detailed and comprehensive information about the study and obtain their written consent.
2. The project coordinator ([name]) will summarize study procedures, risks, compensations, and other relevant information to the participant. Then, the participant will be allowed to fully read the ICF in as much time as they need. The participant may ask questions at any point before or after reading the ICF, after which they will have the chance to sign the document. Participants will be given a copy for their records and will be able to withdraw their consent at any point without penalty.
3. Individuals who are cognitively or decisionally impaired (e.g., dementia, psychosis) will be screened out over a phone call prior to consent procedures. The project coordinator ([name]) will screen interested individuals over the phone.

**D. Alternatives to Participation:** The alternative to participation is to not participate.

**E. Costs to Subjects:** There will be no costs to participants during this study.

**F. How latest information will be conveyed to the study subject and how it will be documented:** Latest information regarding the participants in the study will be conveyed via email. This will be documented in a spreadsheet to ensure that all participants received all necessary information for the study.

**Payment, including a prorated plan for payment:** Participants will be compensated using a prepaid debit card (ClinCard) for their participation in this study. They will receive \$25.00 for completing all assessments at the baseline session. For the weekly training sessions, they will be receive a minimum of \$17.50 for every session they complete. If they complete at least 5 computer training sessions, they will receive \$10.00, and if they complete an additional 5 (i.e., all 10 session), they will be given an additional \$20.00. They will receive \$35.00 for completing the post-training session, \$30.00 for completing the 1-week post-quit date session, and \$30.00 for completing the 1-month post-quit date session. The payment for each of the assessment sessions reflects a \$10 amount to compensate individuals for transportation to the study site.

**A. Payment for a research-related injury:** N/A

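### The 1-week and 1-month smoking outcomes exist only for participants who set a quit date, the post-training visit is ambiguous for early stoppers, and no fallback date is given

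*Combined protocol and SAP*

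**What the plan says.** A person counts as enrolled on signing consent at the baseline session (Study Procedures, Baseline session). None of the three later outcome visits is dated from that point.

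- **Post-training:** "2-3 days following their last training session, participants will complete the DD task, TLFB, TOH, HVLT-R, LNS, and provide a CO breath sample". The quit date is requested at this same visit: "Participants will be asked to set a quit date for their cigarette smoking at this session".
- **1 week:** about 7 days after the quit date.
- **1 month:** "Around 30 days after their quit date, participants will complete the DD task, TLFB, TOH, HVLT-R, LNS", with breath and saliva samples.
- **Length of follow-up (II.B):** "participants will be assessed through their 1-month quit date".

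The Timeline table adds no calendar date. The other place where a quit date is scheduled is group Session 3. Access to the groups depends on training ("After participants complete 5 or more of the working memory trainings, they can begin attending a weekly 60-minute group"), and participants choose how many groups to attend.

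The plan foresees incomplete training. The payment paragraph in section III has separate bonuses at 5 and at 10 sessions ("If they complete at least 5 computer training sessions, they will receive" the first of them). Under II.D item 3, "The researcher reserves the right to discontinue individuals who evidence inability to comply to study conditions". The COVID-19 safety procedures and II.L item 3 give further grounds for ending participation. None of these places describes assessment after stopping.

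II.C counts the sample as 15 completers, without defining a completer. V.B ends the study once 10 people have complete data, and judges success on cigarette use over time. V.A relies on hierarchical linear modelling, partly because it copes with missing data. No analysis set, missing-as-smoking rule or sensitivity analysis is named.

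**The concern.** The two visits that show whether people stopped smoking exist only for those who set a quit date. Setting one is itself a step towards quitting and plausibly related to later smoking. Someone who is asked and does not set a date has no 1-week or 1-month assessment, and the plan does not say how that person enters the result.

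The post-training visit has a related gap. The plan does not say whether the last training session means session 10 or the last one attended, so the visit has no clear date for someone who stops after, say, session 4.

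At stake is the smoking estimate by which V.B judges success and which V.D intends to carry into a grant application. With no comparison group analysed, nothing else in the design would reveal that the post-quit figures describe a selected subgroup.

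**Working it through.** There is no power calculation to reproduce: II.C justifies 15 only as a pilot size and gives no alpha, effect size or dropout rate. The check is therefore of the visit schedule, followed by illustrations on assumed figures.

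**1. Scheduled smoking measures (Timeline Followback and breath CO) per person, from Study Procedures**

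| Participant | Baseline | Post-training | 1 week and 1 month | Total |
|---|---|---|---|---|
| All 10 sessions, quit date set | 1 | 1 | 2 | 4 |
| All 10 sessions, no quit date | 1 | 1 | 0 | 2 |
| Stops after 5 to 9 sessions, sets a date in group | 1 | 0 or 1 | 2 | 3 or 4 |
| Stops early, no quit date | 1 | 0 or 1 | 0 | 1 or 2 |

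The 0 or 1 depends on how the last training session is read. Someone who stops before session 5 cannot join a group, so can reach a quit date only if the post-training visit is held.

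**2. Timing for early stoppers.** Training runs 2 to 3 times a week, so sessions are on average 7/3 = 2.3 to 7/2 = 3.5 days apart. The post-training visit is due 2 to 3 days after the last session. That is about when the next session would be due, so staff may not yet know that a session was the last.

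**3. What the hierarchical model can do.** Its handling of missing data rests on missingness at random: given the values observed, people without post-quit data would have followed the same course as those with them. Here the values are missing because no quit date was set, which makes that doubtful.

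A simulation shows the consequence. All inputs are assumed: 25 enrolled; 15 set a date and fall from 12 to 4 cigarettes/day; 10 set none and are at 12 at the last two visits; everyone is at 11 at post-training; random-intercept model; 60 runs. The expected change at 1 month over all enrolled is (15 × (−8) + 10 × 0)/25 = −4.8.

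| Data used | Mean estimated 1-month change |
|---|---|
| Everyone measured at every visit | −4.7 |
| No-date group gives baseline and post-training | −7.9 |
| No-date group gives baseline only | −7.9 |
| Quit-date setters only | −7.8 |

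Under these assumptions, keeping the post-training values does not remove the bias in the post-quit estimate.

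**4. Size for abstinence.** If a share d of those enrolled has no post-quit data and all of them smoke, the observed rate is 1/(1 − d) times the all-enrolled rate.

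- Assumed example with 15 enrolled and 5 missing: 4/10 = 40% against 4/15 = 26.7%, a ratio of 1.5.
- On the plan's own base of 15 completers, with an assumed 3 abstinent (3/15 = 20.0%), enrolled numbers are 15/(1 − d), rounded up:

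| Assumed d | Enrolled | Abstinent among enrolled |
|---|---|---|
| 10% | 17 | 17.6% |
| 20% | 19 | 15.8% |
| 30% | 22 | 13.6% |
| 40% | 25 | 12.0% |
| 50% | 30 | 10.0% |

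- On the base of 10 with complete data and 3 abstinent (30.0%), enrolled numbers over the same range of d are 12, 13, 15, 17 and 20. The rate becomes 25.0%, 23.1%, 20.0%, 17.6% and 15.0%.

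**The case against.** This is an open-label Stage 1a pilot in people who say they want to quit, and dating post-quit visits from a quit date is a natural and declared choice. Several features also keep more people in view than the schedule first suggests, and they rule out three stronger readings.

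- **That people without a quit date have no follow-up at all.** The request is made at the post-training visit, which itself collects Timeline Followback and CO. Someone who finishes training and declines a date therefore has a follow-up smoking value.
- **That early stoppers necessarily miss the post-training visit.** Everyone who trains has a last session, attendance is monitored, and section III pays for this visit without requiring 10 sessions. Nothing says that 2 to 3 days is a closing window. The session-gap arithmetic shows ambiguous timing, and loss of the visit would be an inference. Those who stop after 5 to 9 sessions can still set a date in group Session 3.
- **That the whole smoking result comes only from people who tried to quit.** A model of cigarette use over time also uses baseline and post-training values from others, and setting a date is not the same as trying to quit.

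It is also fair that every rate used above is assumed, and that the 15 in II.C are completers, not people enrolled.

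All of this narrows the point. None of it supplies a date for someone without a quit date, defines the last training session, or says how people without post-quit data enter the result.

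**Conclusion.** The point holds for the 1-week and 1-month outcomes. They are selected on setting a quit date, the plan offers no fallback, and counting completers or complete data reinforces the selection. For the post-training visit the defect is an undefined anchor for people who stop before session 10, which is not the same as exclusion.

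The size cannot be derived from the documents. If people without post-quit data all keep smoking, the observed abstinence rate is too high by a factor of 1/(1 − d): about 1.1 at d = 10% and 2 at d = 50%. Smoking among those without data is the unfavourable extreme; any of them who stopped would shrink the gap. The direction, a result that looks too good, is likely but not certain.

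This should be corrected before the smoking result is relied on. It does not invalidate the pilot's feasibility aims.

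**What to change.** Amend II.B, II.D item 3, the post-training, 1-week and 1-month paragraphs of Study Procedures, and the Timeline so that stopping training does not by itself end assessment. The change concerns assessment dates only. It leaves alone how training is stopped and how a quit date is agreed.

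1. Invite to all three later assessments every consented participant who has not withdrawn consent and whose participation has not been ended under the COVID-19 safety procedures or II.L item 3.
2. For anyone without a 10th session, hold the post-training assessment once the training window has passed.
3. For anyone without a quit date, hold the last two assessments on pre-set days from baseline. Assume training starts at baseline, the post-training visit is 3 days after the window, and a nominal quit date is 7 days later:
   - 5-week window: 35 + 3 = day 38, nominal quit date day 45, assessments on days 45 + 7 = 52 and 45 + 30 = 75.
   - 3-week window: 21 + 3 = day 24, nominal quit date day 31, assessments on days 31 + 7 = 38 and 31 + 30 = 61.
   - Choose one set in advance.
4. Report abstinence with all enrolled participants as the denominator, beside the completer result. State how missing values are counted.
5. Record whether a quit date was set and why training stopped.
6. Define a completer, and reconcile the 15 in II.C with the 10 in V.B.

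The cost is a short amendment, some staff time to contact people who stopped, and visit payments at the section III rates: at most $35 + $30 + $30 = $95 per extra attendee. The smoking result will probably look less favourable.
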